**Official Title of Study: Protocol for Phase 2 Historically Controlled Trial of
Corticosteroids in Young Boys with DMD**

NCT Number: NCT02167217

IRB Approval Date: 10/2/2013

Protocol for Phase 2 Historically Controlled Trial of Corticosteroids in Young Boys with DMD

MDA grant submission Revised 5/28/2013

PI: [name]

**STUDY COORDINATING CENTER: Washington University School of Medicine in
Saint Louis, [name] [contact])**

Co-Investigators:

[name], Nationwide Children's Hospital
[name], University California Davis
[name], University Texas South Western
[name], Nemours Hospital, Orlando, FL

Statistician:

[name] Washington University School of Medicine

Data Management Site:

Nationwide children's Hospital ([name])

TABLE OF CONTENTS

Title Page.....	page 1
Table of Contents.....	page 2
Protocol Signature Page.....	page 3
Introduction/Background/Rationale.....	page 4
Study Design/ Objectives.....	page 6
Subject selection criteria.....	page 8
Inclusion criteria	
Exclusion criteria	
Recruitment and statistical consideration.....	page 8
Study Procedures.....	page 9
Enrollment and informed consent	
Study Visit description	
Schedule of Events	
Data Management Repository.....	page 11
Technical approach to Data Transfer	
Data Management & Procedures for maintaining confidentiality.....	page 11
Adverse events reporting.....	page 14
Assessment of Risks and Benefits.....	page 14
References.....	page 15

Purpose of this Trial

The purpose of this trial is to determine if weekend oral corticosteroids improve development in infants and young boys with Duchenne Muscular Dystrophy (DMD). We will compare the development of infants and young boys with DMD who are treated with prednisone (10 mg/kg/week given in equal doses over two days) to the development of untreated DMD infants and young boys who have just completed one-year follow-up using the same measures. Gross motor development, fine motor development, speech, language and social skills will be assessed at baseline, and after six months and twelve months treatment.

Introduction/Background/Rationale

Duchenne Muscular Dystrophy is an X-linked, genetic disorder. The clinical picture consists of progressive proximal muscular weakness, which leads to loss of ambulation with subsequent loss of hand and arm function and respiratory and cardiac failure.

The early careful natural history studies of boys with DMD relied on manual muscle testing using medical research council (MRC) testing and functional outcomes¹⁻³. These outcomes have been extended to include quantitative measurements, which allow better inter-rater reliability for ambulatory boys and are currently used in multicenter trials⁴⁻⁸. Additional functional measures including activity monitoring are very useful for ambulatory boys⁹.

However, few trials have used younger boys who are unable to be tested using traditional MRC or quantitative testing. Prior studies demonstrate effectively the “honeymoon” period in DMD when absolute function and strength may improve^{1, 10}. However, the improvement does not equal that seen in normal children, as they remain weak compared to their peers. A pilot study of baseline motor function in 33 young boys with DMD (mean age 3.4 years) shows markedly different gross motor skills from age-matched controls using the Hammersmith Motor Ability Score¹¹. The same study showed the locomotor quotient of the Griffiths’ scales demonstrated deterioration in young boys with DMD¹¹. This latter measurement showed a highly significant negative correlation with age. The Bayley infant motor scale (used from birth through 42 months), has been validated in dozens of studies of children with motor delay in the first years of life¹²⁻²⁰. Furthermore, it has an advantage in that clinical evaluators (CEs) can be trained in its use.

The MDA funded DMD center network recently completed baseline assessment of 24 infants using the Bayley-III, the HFMSE, and the North Star Ambulatory Score to assess infants from age 3 months through 2.9 years. One year follow up studies of 20 of these children are complete. Once ambulatory, boys were also able to complete the early motor skills of the North Star Ambulatory Assessment (NSAA) which has been validated in older boys with DMD.

Here we propose to use the Bayley-III and the North Star Ambulatory as outcome measures in a phase 2 historically controlled trial in infants who are age 3 months through 30 months at enrollment in a multicenter trial using the 5 DMD-MDA funded sites.

Imaging of muscle in DMD. Imaging of muscle as a marker of disease progression in

DMD has been considered for some time. Marden et al demonstrated that high resolution MRI could distinguish boys less than age 10 who were still ambulatory ²¹. Recently, [name], a child neurologist at Washington University has studied ultrasound as a marker of disease in boys with DMD ²². Calculated muscle backscatter (cMB), an ultrasonic measure muscle damage increases with age, even during the “honeymoon period” before age 8 years when absolute strength continues to increase. Additional data obtained from untreated infants with DMD demonstrates that the linear increase in backscatter extends into the first year of life. This suggests that ultrasound may be an excellent, non-invasive marker of this disease. This will form a secondary outcome for this study.

Electronic Impedance Myography.

Electrical Impedance Myography (EIM) is a new approach to the assessment of muscle and neuromuscular disease, the development of which has been spearheaded by [name] at Beth Israel Deaconess Medical Center in Boston ²³. In EIM, very low-intensity, high-frequency electrical current is applied via surface electrodes and the consequent surface voltages are measured. The electrodes are non-invasive and do not require any special procedure to apply. Results thus far in a variety of disease contexts confirm that EIM is very sensitive to localized changes in muscle health and will serve as a new quantitative approach to monitoring disease states and responses to medical or rehabilitative therapies²⁴⁻³⁰. Since the test is entirely painless, non-invasive, and independent of patient effort it has the potential of finding wide clinical utility.

Thus, in 2006, with the funding support of the Center for Integration of Medicine with Innovative Technology (CIMIT), [name], in collaboration with [name] in the Electrical Engineering and Computer Science Department of the Massachusetts Institute of Technology, began to develop a new handheld-system. The initial design was completed in late 2008 and initial data were obtained in 2009 through 2010 using this system. The data obtained with this handheld EIM approach were very promising, showing marked alterations in the data in 2 different types of disease states (neurogenic and myopathic) as compared to that seen in normal subjects. The devices developed by Convergence Medical Devices, Inc. have been used on over 60 individuals, including infants, and there have been no related adverse events (AEs) (serious or otherwise) to date.

We plan to measure EIM from the surfaces overlying proximal and distal muscles of the arm and leg in infants during each study visit. We will compare changes in EIM to other outcome measures overtime. Examination of a muscle with EIM takes seconds. We therefore anticipate being able to examine several muscles without undue burden on the infant subject. Furthermore, EIM is entirely painless and requires only passive involvement of the infant. We therefore do not anticipate any complications or discomfort from the performance of EIM on the infant.

The physical risks to the study subjects are extremely low because the studies utilize electrical currents of extremely low intensity and do not produce any pain (in fact, one does not feel anything outside of the light pressure of the probe against the skin). The

devices will run off regular household batteries with a maximal current output of 0.2 mA (rms), thus virtually ensuring no risk of electrical shock. Still, there is the risk that the repeated placement of electrodes could irritate or redden the skin and may feel somewhat uncomfortable. Although care will be taken to prevent this, some irritation is potentially possible.

Mental development of young DMD boys. Cyrulnik et al demonstrated that cognitive delay is clearly recognized by parents³¹. Hinton et al have also characterized verbal and memory skills in older boys with DMD³². The earliest study of mental development in young boys with DMD (6 boys who were a subset of Brooke et al's original study) was accomplished using the Denver developmental assessment^{1 33}. However, because the Denver assessment does not provide a quotient it is not possible to quantify the delays. Detailed work in mental development of young boys with DMD has been reported by Smith et al using the Griffith's Mental Development Scales (GMDS)³⁴. However, this scale is not available in the United States and requires administration by a psychologist.

The most validated, commonly used scales of language and cognition in all infants and children through age six years are the Bayley scales of infant development (Bayley-III) (valid through 42 months)³⁵ and the Stanford Binet Intelligence Scale 5th ed. (ages 3 years and up)³⁶. Both provide measurable quotients. The Bayley-III has been used in studies of children at risk for both motor and mental delays including premature infants, children with hypoxic ischemic injuries, children with Down's syndrome and children with immune deficiency¹²⁻²⁰. We also recently completed evaluation of 24 infants and young boys with DMD using the Bayley-III

Treatment of children with DMD with twice weekly oral prednisone (10mg/kg/week) is safe and effective in improving strength in both boys with DMD and the mdx mouse model. There is preclinical data demonstrating that weekly oral prednisone improves strength and prolongs life of the mdx mouse^{37, 38}. A pilot study by Connolly et al demonstrated a favorable side effect profile with no increased risk of obesity and maintenance of linear growth with improved strength and function compared to historical control boys with DMD who were not treated⁵. The follow-up study, a randomized, blinded, controlled study of daily versus high dose weekly corticosteroids showed both were equally efficacious in improving strength and function in ambulatory boys with DMD³⁹. Here we propose to use the weekly regimen in young infants who would not tolerate the cumulative effects of daily corticosteroids. Participants will be given prednisone at their first visit and will be instructed to start administration of drug on the weekend. Drug will be given to them at every visit at no cost to them.

Study objectives and Design

Objective 1. Establish gross motor development as a valid outcome measure in young boys with DMD at the 5 MDA-DMD centers. Preliminary data show that average gross motor function in infants and young boys with DMD declined over six and 12 months compared to age matched peers when assessed using Bayley-III Scales of Infant Development (Bayley-III). Fine motor, cognitive, and language skills did not

decline.

Aim1a. Continue Validation of Bayley-III as an outcome measure in infants with DMD. We will train/retrain Clinical Evaluators (CE's) from the 5 MDA-DMD centers in this assessment tool.

Aim1b. Continue validation of the North Star Ambulatory Assessment (NSAA) in the youngest ambulatory boys with DMD. We will train/retrain CE's from the 5 MDA-DMD centers in this assessment tool.

Aim 1c. Establish age of independent walking as a valid outcome in infants with DMD. The precise age of walking for young boys with DMD has not been established in a prospective fashion. For those children already walking we will ask for the age at independent walking defined as 10 independent steps. For those who are not yet walking, we will prospectively capture this information in this study.

Objective 2. Determine if twice-weekly high dose oral prednisone improves gross motor development in infants and young boys with DMD. We will perform a phase 2 historically controlled trial of oral twice-weekly prednisone (5mg/kg/dose on two consecutive days) in infants and young boys with DMD. Here we propose to study the effect of this therapy in a multicenter trial of boys with DMD who are less than 30 months old at the baseline visit. Each boy will be followed for one year.

Aim2a. Determine if treatment improves gross motor function in infants with DMD over a 6-12-month period as measured by the Bayley-III. The Bayley-III infant score is the primary motor clinical endpoint of this therapeutic trial. Secondary outcomes include fine motor function, speech and language, and social function.

Aim 2b. Determine if treatment improves the Adaptive Behavior Subtest of the Bayley-III (ABS) as scored by the infants' primary caregiver. In the study of untreated boys, the primary caregiver noted clear deficits, predominantly related to areas relevant to gross motor function. The ABS

Aim 2c. Determine if treatment improves performance on the NSAA for those boys who are ambulatory.

Aim 2d. Determine if treatment with weekly corticosteroids is tolerated and is safe in boys with DMD who are less than 30 months of age.

Objective 3. Determine if ultrasound or Electronic impedance Myography (EIM) of biceps and quadriceps improves in infants and young boys with DMD who are treated with oral high dose weekly corticosteroids 3A. **Determine if ultrasound using calibrated backscatter improves in infants and young boys treated with DMD.** Preliminary data of ultrasound imaging in infants and young boys with DMD demonstrate progressive structural damage as measured by calibrated backscatter. The ultrasound studies will be limited to the infants and boys who will enroll at the primary site (Washington University) where [name] has the equipment and expertise to accomplish this aim. 3B. EIM is a new approach for the assessment of muscle and has been shown to distinguish normal muscle from diseased muscle. EIM is a very low-intensity high-frequency electrical current is applied via surface electrodes and the consequent surface voltages are measured. The electrodes are non-invasive and do not require any special procedure to apply.

Objective 4. Determine if caregiver burden changes with treatment of infants and young boys with DMD. Preliminary data from questionnaires suggests the caregiver burden for the primary caregiver of untreated infant and young boys with DMD is minimal. Assessment of this with in this trial will allow us to discern if this changes with a therapeutic trial.

Subject selection criteria

Inclusion Criteria

Clinical Diagnosis of Duchenne Muscular Dystrophy. This must be confirmed in one of two ways

1. Appropriate degree of weakness for age, creatine kinase >20X the upper limit of normal, and genetic mutation known to be causative for DMD.
2. Appropriate degree of weakness for age, creatine kinase >20X the upper limit of normal and genetic or biopsy confirmation of Duchenne muscular dystrophy in a primary relative (e.g. brother or maternal uncle)
3. De-identified, genetic studies will be reviewed by collaborator [name] prior to enrollment of subjects.
4. Age at entry: one month through 30 months

Exclusion Criteria

Glucocorticoid treatment

Recruitment of infants and young boys: We will enroll children from age 1 month through age 30 months. Follow-up examinations will be performed 6-month and 12 months after the baseline visit. The specific goal would be to determine whether the average change in Bayley-III scores differ from the scores of the boys who are untreated. A total of 25 children will be needed and we expect to follow them every 6 months for one year. Based on the recruitment in the study of untreated infants we expect to recruit these children over 15-24 months. We are allowing for a potential drop out of 5 infants.

Statistical considerations and Power Calculations for current study.

Follow-up of twenty untreated infants and young boys with DMD showed that the average negative change in the Bayley III gross motor scaled score over six months was -0.4. If the effect size of therapy is an increase of 1.5 points on this scaled score, then 19 infants would be required for 95% confidence to detect a difference. If the effect size of corticosteroids is +2.0 points only 11 infants would be required. We have chosen to enroll 24 infants, with the expectation that 4 might be lost to follow up or drop out of the study. While we have calculated the effect size for six months, additional data in a small subset suggest there is further decline over 12 month (total average decline of 1.0 point in 12 boys. The six month and 12 month follow-up of the cohort will be analyzed and reported to the MDA.

Study Procedures and Visits

The fundamental goal of this work is to determine if two reliable developmental assessments (Bayley-III and NSAA) in young boys with DMD will detect a change in gross motor function in infants and young boys treated with twice weekly oral prednisone. We will follow children for one year and they will be ages 1 month through 30 months at enrollment.

There will be a total of six visits, Baseline, and at 1, 3, 6, 9, and 12 months.

Baseline evaluation and visits at 6 and 12 months will include:

a) History to include age of walking defined as 10 independent steps

b) Every 6 months Vital signs including height, weight, heart rate, blood pressure

Height will be assessed in two ways

1. Measurement of supine length if child is not able to stand

2. Standing height if child is able to stand

c) Every 6 months the following will be performed

1. Bayley-III Scales of Infant Development.

This test consists of a standardized assessment of cognitive, language, and motor using small toys, blocks and books. For infants there is a special set of activities to assess the muscle function called Bayley-III infant motor scale which has both a fine motor and gross motor component. This assesses the degree of body control, large muscle coordination, finer skills of the hands and fingers, dynamic movements. This will be done through observations and questions. The Bayley-III infant mental scales will test language and cognition.

2. North Star Ambulatory assessment North Star Ambulatory Assessment

(NSAA). The NSAA^{40, 41} assesses functional activities including standing, getting up from the floor, negotiating steps, hopping, and running. The assessment is based on a 3 point rating scale of 2= ability to perform the test normally, 1= Modified method or assistance to perform test, 0=unable to perform the test. Thus, total score can range from 0 (completely non-ambulant) to 34 (no impairment on these assessments).

3. Ultrasound of the muscle (this measure will be followed only on infants recruited from the Washington University Site)

This will be done by keeping the ultrasound probe on biceps and quadriceps to see the image of the muscle for structural changes. As the muscle changes the ultrasound will reflect the changes.

4. EIM of Muscle. This will be performed at all sites

5. Behavior: The Adaptive Behavior Assessment Scale (ABAS) is a well-validated measure of adaptive behavior and will be tested every 6 months.

6. Caregiver Burden: This will be tested by filling out the Caregiver stress questionnaire.

7. Complete Physical Examination and Neurological examination

The Visits at 1, 3, and 9 months will be safety visits which can be performed locally or on site. If laboratory studies are performed locally, phone visit will occur.

Table 1. Schedule of Events

Study Period (+7 days)	Month 0	Month 1*	Month 3*	Month 6	Month 9*	Month 12
Informed consent	X					
Vital signs, Height, Weight, Occipital Frontal Circumference BMI (kg/m ²)	X			X		X
Medical History	X	X	X	X	X	X
Medication review	X	X	X	X	X	X
Con Medication review	X	X	X	X	X	X
Medical Events		X	X	X	X	X
Adverse Events		X	X	X	X	X
Physical examination	X			X		X
Neurological Examination	X			X		X
Electronic Impedance Myography	X			X		X
Ultrasound for WU infants only	X			X		X
North Star Ambulatory Assessment	X			X		X
Bayley-III Scales of Infant development	X			X		X
Adaptive Behavior Assessment Scale	X			X		X
Care giver Burden assessment	X					X
CBC/Diff	X	X	X	X	X	X
CPK	X	X	X	X	X	X
Sodium	X	X	X	X	X	X
Potassium	X	X	X	X	X	X
Chloride	X	X	X	X	X	X
CO ₂	X	X	X	X	X	X
BUN	X	X	X	X	X	X
Fasting Serum Glucose	X	X	X	X	X	X

**Phone call or on site assessments will take place at visits 1, 3, and 9 months.

Criteria for dose reduction:

Prednisone dose will be reduced for

- 1) An increase in Body mass index (BMI) (kg/m²) greater than 10% over 6 months
- 2) A fasting blood sugar greater than 100mg/dl after dietary modification
- 3) An increase in diastolic blood pressure greater than 10mm Hg over upper limit of normal for age
- 4) An increase in systolic blood pressure greater than 15mm Hg since the last visit
- 5) Otherwise, non-manageable side effects including irritability or difficulty sleeping.

Data Management Repository

The informatics component of the proposed specific aims will provide a centralized data management repository. The system will provide a secure web-based application designed to harmonize data from the all-participating institutions. The functionality of the system will include data entry, data integration, data validation and quality control, searching, reporting, and exporting. The system will have three core components to include administration, institution, and investigator data requests. The administration component will allow a defined member of the MDA DMD CRC Network access to data generated from their sites and data from the network at large, upon validation that data request forms are from participating institutions. The approval process will be defined in the Manual of Operations. Once approved, the data set is generated and released to that approved investigator. **The data that will be submitted to the central data management repository will include the following information.**

1) Demographics

- ID#
- Date of Birth
- Date of study visit
- DMD Gene Mutation
- Age (derived from DOB, Date of study)
- Height/Length in centimeters
- Weight in kilograms
- Body Mass Index
- Occipital Frontal Circumference in centimeters

2) Assessments

- a) Bayley-III scales of Infant Development
 - b) North Star Ambulatory Assessment
 - c) Adaptive Behavior Assessment Scale (ABAS)
 - d) Caregiver Burden
- 3) History including Dietary history recorded
 - 4) Medical events recorded
 - 5) Adverse events recorded
 - 6) Concomitant medications recorded

Time expected to complete these visits will vary somewhat depending on the subjects' own strength and function. The predicted time to complete all procedures and

questionnaires is 2-3 hours.

Data Management

A centralized data management repository will be used for this study. The system will provide a secure web-based application designed to harmonize data from all participating institutions. The functionality of the system will include data entry, data integration, data validation and quality control, searching, reporting, and exporting. The system will have three core components to include components to include administration, institution, and investigator data requests. The administration component will allow a defined member of the MDA DMD CRC Network access to data generated from their sites and data from the network at large, upon validation that data request forms are from participating institutions. The approval process will be defined in the Manual of Operations. Once approved, the data set is generated and released to that approved investigator.

Procedures for maintaining confidentiality

Institutions participating in the DMD Clinical Outcomes Project including Washington University in Saint Louis, Nationwide Children's Hospital in Columbus Ohio, University Texas Southwestern, Nemours Children's Hospital, Orlando Florida, and University of California Davis will collect the necessary data as defined in the Manual of Operations. Patients and the supporting data will be de-identified at each given site using a defined identifier schema satisfying HIPAA requirements prior to submitting study data to the informatics Core. As each case is being completed the participating institution will securely submit to the data center the case report forms utilizing a secure file transfer protocol (SFTP) incorporating technology providing encrypted channels, preventing passwords and sensitive information from being transmitted via the Internet.

Adverse events reporting:

Adverse events in this trial to validate outcomes will be reviewed within 24 hours by the PI at each site who will be responsible for reporting such events and communicating those events to the primary PI, **[name] [contact] Work) or [contact] (Cell phone).**

Assessment of Risks

Risks of oral weekly Prednisone

Likely: Mild irritability or sleep disturbance on the days prednisone is taken. Some children may experience increased hunger on the days prednisone is taken

Less Likely: Corticosteroid use may decrease the immune response. With intermittent use proposed in this study, this risk is less common. Some children may develop stomach pain or discomfort. Some children may develop excessive weight gain

Rare: Rarely, children may develop intestinal bleeding. Rarely, children may develop adrenal suppression. While this is common in children taking daily corticosteroids it is rare with the weekend dosing regimen. This will be tested for with safety laboratory tests at baseline, 1, 3, 6, 9, and 12 months.

Risks of Muscle Testing.

Likely: Muscle fatigue.

Less likely: None Known.

Rare: None Known.

Risks of Language and Cognitive Assessments:

Likely: Some children may feel uncomfortable with the evaluator.

Less Likely: None Known.

Rare: None Known.

Risk of Ultrasound of muscle:

Likely: Irritation or rash at the probe site.

Less Likely: None Known.

Rare: None Known.

Risk of Electronic Impedance myography:

Likely: Irritation or rash at the probe site.

Less Likely: None Known.

Rare: None Known.

Risk of Blood Draws:

Likely: Bruising at site

Less likely: Fainting

Rare: Local infection

Patients may experience all or some of the risks listed above. There may also be unknown risks. The PI will be responsible for any questions subjects have about these risks.

Assessment of Benefits

There is abundant evidence in older children that oral corticosteroids improve strength and function. There is also emerging evidence that those treated early with corticosteroids may have benefits many years later with prolonged walking. The direct benefit may be improvement in motor development. There may also be an improvement in behavior as this was also seen in the randomized trial of daily versus weekly corticosteroids. It is hoped that the knowledge gained from this study will help us know if this group of infants can be reliable subjects in other clinical trials.

Decision to discontinue treatment

If the family decides to discontinue corticosteroid therapy they will be given the option to continue to be followed using the same clinical outcomes described above.

References:

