Statistical plan for
Historically Controlled Trial of Corticosteroids in Young Boys With
Duchenne Muscular Dystrophy

Statistics will be performed with Excel (Microsoft Inc.) and GraphPad Prism (GraphPad Software, La Jolla, CA). P-values will all 2-tailed. A p value of <0.05 will interpreted as showing statistical significance. Mann Whitney U will be used for non-parametric data.

Analysis of data will be performed in two ways. First, the change over one year in the Treated Cohort will be compared to the previously published Historical Control Cohort (HCC). Second, repeated measures (paired t- tests) were used to analyze each boy's performance over his own baseline.

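### The one-year between-cohort test can use only boys with a month-12 score and has no missing-data rule, although 17–20% treated loss is expected; month-6 scores stay outside that test and the control count at month 12 is unclear

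*Protocol*

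**What the plan says.** The SAP names two analyses. In the first, "the change over one year in the Treated Cohort will be compared to the previously published Historical Control Cohort (HCC"; in the second, paired t-tests set each boy against his own baseline. Mann-Whitney U is named for non-parametric data. The SAP defines no analysis set, no missing-data rule and no longitudinal model.

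The protocol's section on statistical considerations and power enrols 24 boys "with the expectation that 4 might be lost to follow up or drop out of the study". The recruitment paragraph just before it gives 25 boys and an allowance of 5. Table 1 schedules Bayley-III at months 0, 6 and 12, and the power section says both follow-up points will be analysed and reported to the funder.

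On the controls, the protocol's introduction reports 24 boys assessed at baseline and one-year follow-up complete in 20. The power section describes six-month change in twenty boys and, from a small subset, a "total average decline of 1.0 point in 12 boys".

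Under the heading on discontinuing treatment, families who stop corticosteroids learn that "they will be given the option to continue to be followed". The SAP does not say whether those boys' later scores count in the treated cohort.

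**The concern.** A one-year change cannot be computed without a month-12 score, so the between-cohort test as written rests on completers. The SAP does not say so; it follows from the test. Enrolling extra boys protects the number analysed, not against selective loss. The protocol lists irritability, disturbed sleep and weight gain among the risks of prednisone, and follow-up after stopping is optional, so selective loss is plausible. If boys who do poorly leave the treated cohort, its mean looks too good and the comparison favours prednisone. If poorly performing controls are the ones without month 12, the control mean looks too good and the benefit is understated. With no randomisation to lean on and about 20 boys per cohort, either shift matters. The month-6 scores could reduce both the bias and the loss of precision, but the stated one-year test has no place for them.

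**Working it through.** **Loss fractions, from the protocol's counts.** Treated: 4/24 = 16.7% or 5/25 = 20.0%. Controls without month 12: (24 − 20)/24 = 16.7% from the introduction, or (24 − 12)/24 = 50% if the 12 boys in the power section are set against the 24 at baseline.

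**The plan's own sample size.** The protocol asks for 19 infants for a 1.5-point effect and 11 for 2.0 points, calculated for six months. It states neither SD nor power: "then 19 infants would be required for 95% confidence to detect a difference" gives only a confidence level. The SAP sets two-sided testing at 0.05. Assuming 80% power and a two-sample t-test with equal groups, SD 1.58 fits both figures: for 1.5 points, power is 81% with 19 per group and 79% with 18; for 2.0 points it is 81% with 11. This back-solved SD is an assumption; at 90% power an SD of about 1.35–1.375 would fit instead. With 24 − 4 = 20 boys left against 19 required, the treated count is covered.

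**Precision.** Further assumptions: 22 treated boys have month 6 and 20 have month 12; the SD and the 1.5-point effect carry over to one year; the correlation r between six- and twelve-month change is 0.5–0.8. For each cohort:

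- completers: variance = SD²/n12
- all visits: variance = SD²[(1 − r²)/n12 + r²/n6]

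Here SD² = 2.4964. Power is t-based, with the completers' degrees of freedom (30 or 38).

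*12 controls at month 12, 20 at month 6.*
- Completers: 2.4964 × (1/20 + 1/12) = 0.3329, SE 0.577, power 71%.
- r = 0.5: treated 2.4964 × (0.75/20 + 0.25/22) = 0.1220; controls 2.4964 × (0.75/12 + 0.25/20) = 0.1872; sum 0.3092, a cut of 7%, power 74%.
- r = 0.8: treated 2.4964 × (0.36/20 + 0.64/22) = 0.1176; controls 2.4964 × (0.36/12 + 0.64/20) = 0.1548; sum 0.2723 (rounded from unrounded terms), a cut of 18%, power 79%.

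*20 controls at month 12.*
- Completers: 2.4964 × (1/20 + 1/20) = 0.2496, SE 0.500, power 83%.
- Least gain (20 controls with month 6, r = 0.5): 0.1220 + 0.1248 = 0.2468, a cut of 1%, power 84%.
- Most gain (24 controls with month 6, r = 0.8): 0.1176 + 2.4964 × (0.36/20 + 0.64/24) = 0.1176 + 0.1115 = 0.2291, a cut of 8%, power 86%.

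**Bias.** Suppose the log-odds of loss rise by 0.5–1.0 per SD of poorer month-6 change (odds ratios 1.6–2.7), with r = 0.5–0.7. The completers' mean in that cohort is then off by r × SD × m, where m is the mean standardised month-6 change among boys retained, found by numerical integration.

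| Loss | m (slope 0.5; 1.0) | Lowest shift | Highest shift |
|---|---|---|---|
| 16.7% | 0.0805; 0.146 | 0.5 × 1.58 × 0.0805 = 0.06 | 0.7 × 1.58 × 0.146 = 0.16 |
| 20% | 0.096; 0.173 | 0.5 × 1.58 × 0.096 = 0.08 | 0.7 × 1.58 × 0.173 = 0.19 |
| 50% | 0.236; 0.413 | 0.5 × 1.58 × 0.236 = 0.19 | 0.7 × 1.58 × 0.413 = 0.46 |

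For scale, the protocol gives an untreated decline of 0.4 point at six months and 1.0 at twelve. A separate simulation (SD 1.64, no true effect, r = 0.5–0.7, slope 1, month 6 known for every boy) agrees on direction. The completers' contrast was +0.13 to +0.18 when only the 4 treated losses were selective, and −0.32 to −0.44 when only the losses of 8 of 20 controls were. An all-visits estimate was close to zero in each case, as expected when loss depends only on an observed score.

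**The case against.** Three stronger readings are tempting, and the documents do not support them.

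- A reader might infer that half the controls are expected to be lost. Nowhere is control loss expected. The introduction has one-year follow-up complete in 20 of 24, and the statement of purpose describes controls who have just completed it. The 12 boys are called a subset and may be an interim count. Half is the worst case of an unreconciled range.
- A reader might infer that month-6 scores are thrown away. The protocol says both time points will be analysed, and the gross motor aim covers six to twelve months. What is missing is a method that uses both visits in the one-year comparison.
- A reader might infer that the paired t-tests also drop every boy without month 12. The SAP fixes no visit for them, and a paired test at month 6 would keep boys lost later.

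Other objections stand in part. The loss allowance belongs to a six-month calculation and leaves enough treated boys. With 20 controls at month 12, the gain in precision is small. The bias figures assume loss driven by month-6 change, the setting in which a mixed model works best; it cannot repair loss before month 6 or loss driven by unobserved scores. On the assumed path, two of the four treated losses have no month-6 score. None of this supplies the missing rule, or protects the one-year test from selective treated loss.

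**Conclusion.** The point holds in this limited form. The one-year between-cohort test is a completers' test by construction, foreseen treated loss of 17–20% has no handling rule, and available month-6 scores are left out of it. The main risk is selective loss, worth about 0.06–0.19 point in the treated mean on the assumptions above. The range of 0.19–0.46 applies only if half the controls lack month 12. Precision is a serious argument only with 12 controls at month 12 (power 71% rising to 74–79%); with 20 the gain is marginal (83% rising to 84–86%). The SD, power, correlation, dropout slopes and month-6 counts are assumptions. The percentage cuts in variance do not depend on the SD, and the bias figures scale in proportion to it. The change should be made, but the plan does not fail without it.

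**What to change.** - Make the main between-cohort analysis a mixed model for repeated measures on the gross motor scaled scores at months 0, 6 and 12 from every boy in both cohorts. Include cohort, visit, cohort-by-visit and baseline age, allow for within-boy correlation, and estimate the month-12 difference.
- State that boys who stop prednisone but remain in follow-up stay in the treated cohort with all their scores.
- Keep the completers' test as a sensitivity analysis, and add one for data not missing at random.
- Reconcile the introduction (20 controls at one year) with the power section (12), and give control counts at each visit. Settle 24 with 4 lost against 25 with 5 lost.

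The cost is SAP wording and software beyond Excel and Prism's basic tests, with no new data collection if patient-level control scores can be used. The same network collected them, and a Mann-Whitney test of change would need them anyway, but the documents do not confirm their use. The model assumes missing at random and adds nothing for boys lost before month 6.
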